1.5. Schedule of Assessments (MAD)

Table 3: Schedule of Assessments Multiple Ascending Dose Level Cohorts 1 – 6 (MAD) – Screening/Check-in/Day 1

	Screening	CI	CRU Inpatient										
Day	(-30 to -2)	D (-1)	D1 – Initial Dosing Day										
Hour			0	0.25	0.50	1	1.5	2	3	4	6	8	12
Informed consent	X												
Confirm eligibility	X	X ^o											
Demographics	X												
Medical history	X	X											
Full physical examination	X	X											
Neurological examination	X	X											
Height/weight ^a	X	X											
HIV/Hep B/Hep C	X												
CRU Check-in		X											
SARS-CoV-2 PCR ^b		X											
Drug screen ^c	X	X											
Laboratory assessments ^d	X	X								X			X
Urinalysis ^e	X	X								X			
FSH testing ^f	X												
Pregnancy test ^g	X	X											
12-lead electrocardiogram	X	X											
Body composition ^h		X											
C-SSRS	X	X											
LVEF/Echocardiogram	X ⁱ												
Randomization			X										
Cardiac telemetry ^j			←										
Oximetry ^j			←										

	Screening	CI	CRU Inpatient										
Day	(-30 to -2)	D (-1)	D1 – Initial Dosing Day										
Hour			0	0.25	0.50	1	1.5	2	3	4	6	8	12
Vital signs	X	X	X			X	X			X	X	X	X
Plasma PK ^k													
Urine PK ^l			X							X		X	X
Genetic biomarker (buccal swab)		X											
Plasma Biomarker			X			X							
Spirometry		X								X			X
Magnetic stimulated contraction ^p		X								X			
Dynamometry ^p		X								X		X	X
IPSS ^m		X											
Urinary system Ultrasound ⁿ		X											
MTR-601 administration			X										
Adverse events													
Concomitant medications	X	X											

Abbreviations: AE = adverse event; CI = Check-in; CK-MB = creatinine kinase heart; CK-MM = creatinine kinase skeletal muscle; C-SSRS = Columbia Suicide Severity Rating Scale; D = Day; LVEF = left ventricular ejection fraction; PK = pharmacokinetics.

Note: When several assessments overlap, the suggested sequence of events will be as follows: ECG, vital sign collection, PK sample collection, laboratory blood sample collections, spirometry, dynamometry, urinalysis sample collection, and biopsy, such that PK sample collection will be drawn as close to the nominal collection time point as possible.

- Height measured only at screening.
- To be performed as part of check-in procedures, prior to other Day -1 activities.
- Urine drug screen for cotinine, alcohol, and drugs of abuse.
- Laboratory assessments will include serum chemistry, hematology, liver function tests, coagulation, and creatinine kinase (CK-MM and CK-MB). eGFR will use CKD-EPI calculation. For Cohort 3 only, Cystatin C will be measured on Day 1 at 4 and 12 hours and Day 2, Day 8 and Day 14 (all pre-dose).
- Urinalysis by dipstick; if results are abnormal, follow up with microscopy. Samples are to be collected under colored lighting into opaque containers to blind participants to any discoloration of the urine. For Cohort 3 only, urine creatinine, protein, albumin and Kim-1 will be measured at Day -1, Day 1 at 4 hours, Day 15 and Day 16; and urine sediment will be microscopically evaluated at Day -1, Day 7 (pre-dose) and Day 15.
- FSH testing for postmenopausal females only.
- For women of childbearing potential: Serum pregnancy test.
- Body composition assessments by bioimpedance and physical measurements.
- Performed during screening as a secondary visit or up to Day -1 to confirm subject is still eligible.
- Telemetry and oximetry will continue into approximately 24 hours post-dose (Day 2), although it may be interrupted as needed to allow subjects to bathe.

- k. Plasma PK samples for Day 1 (initial dosing day) will be drawn at pre-dose (time 0); and post-dose at 0.25, 0.50, 1, 1.5, 2, 4, 6, 8, and 12 hours.
- l. Urine will be collected for PK analysis on Day 1 from a pre-dose void and post-dose from 0–4 hours, 4–8 hours, and 8–12 hours. Samples are to be collected at intervals under colored lighting into opaque containers to blind participants to any discoloration of the urine.
- m. IPSS questionnaire will be performed at the specified timepoints per SOA- results greater than 8 will necessitate an unscheduled urinary system ultrasound as soon as is feasible .
- n. Urinary system Ultrasound will be performed at specified timepoints in SOA unless the IPSS result (greater than 8) necessitates additional unscheduled ultrasonography.
- o. Screening eligibility will be determined by off-site (LabCorp) Lab Total CK and CK-MB values while check-in eligibility will be determined by Day-1 on-site (WCT) lab Total CK and CK-MB values. .Furthermore, CK isoenzymes (e.g., MM, MB) will not be evaluated as part of dose escalation decisions – rather total CK will be used.
- p. For Cohorts 4-6, Magnetic Stimulated Contraction and Dynamometry time points will be as follows: Day -1, Day 1 (0-2 hours pre-dose), Day 7, Day 8, Day 12, Day 13, Day 14, Day 15.

Table 3 continued... Schedule of Assessments Multiple Ascending Dose Level Cohorts 1–6 (MAD) – Days 2-18 and Follow-up

	CRU Inpatient																FU
Day	Non-PK Days 2–6, 8–13	PK Days 7 and 14											D15	D16	D17	D18	D20
Hour		0	0.25	0.50	1	1.5	2	3	4	6	8	12	0	0	0	0	4
Full physical examination		X														X	
Neurological exam		X														X	
Height/weight ^a		X														X	
Laboratory assessments ^b	X ^k	X											X	X	X	X	
Urinalysis		X											X	X	X	X	
12-lead ECG		X														X	
C-SSRS									X							X	
LVEF/Echocardiogram	X ^c																
Cardiac telemetry ^d																	
Oximetry ^d																	
Vital signs		X			X	X			X	X	X	X	X	X	X	X	
Plasma PK ^e													X	X	X	X	
Urine PK ^f	X	X							X		X	X	X	X	X	X	
Biomarker		X														X	
Spirometry	X ^g								X			X		X		X	
Magnetic stimulated contraction		X							X				X			X	
Dynamometry	X	X							X		X	X	X	X	X	X	
Muscle biopsy ^h		X															
IPSS ⁱ	X									X			X	X	X		X

	CRU Inpatient																FU
Day	Non-PK Days 2-6, 8-13	PK Days 7 and 14											D15	D16	D17	D18	D20
Hour		0	0.25	0.50	1	1.5	2	3	4	6	8	12	0	0	0	0	4
Urinary system Ultrasound ^j	X									X						X	
MTR-601 administration	X	X															
Adverse events																	
Concomitant medications																	
CRU check-out/discharge																X	
Follow-up telephone call																	X

Abbreviations: AE = adverse event; CK-MB = creatinine kinase heart; CK-MM = creatinine kinase skeletal muscle; D = Day; ECG = electrocardiogram; LVEF = left ventricular ejection fraction; PK = pharmacokinetics.

Note: When several assessments overlap, the suggested sequence of events will be as follows: ECG, vital sign collection, PK sample collection, laboratory blood sample collections, spirometry, dynamometry, urinalysis sample collection, and biopsy, such that PK sample collection will be drawn as close to the nominal collection time point as possible.

- Height measured only at screening.
- Laboratory assessments will include serum chemistry, hematology, liver function tests, coagulation, and creatinine kinase (CK-MM and CK-MB). eGFR will use CKD-EPI calculation.
- Echocardiogram performed on Day 6 and Day 13 only, post AM dosing.
- Telemetry and oximetry will continue from Day 1 into pre-dose Day 2; Day 7 into pre-dose Day 8; and Day 14 into Day 15, and for 12 hours post dosing on all other dosing days although it may be interrupted as needed to allow subjects to bathe.
- Plasma PK samples will be drawn at pre-dose (time 0) on Days 7 and 14; post-dose on Days 7 and 14 at 1, 1.5, 2, 4, 6, 8 and 12 hours; (need trough at D14) 336 hours post-dose (Day 15); 360 hours post-dose (Day 16); and 384 hours post-dose (Day 17). For Cohorts 3-6, PK samples will also be drawn on Day 2 and Day 8 (both pre-dose).
- Urine will be collected for PK analysis on 12-24 hours post-dose on Day 2; Day 7 and 14 from a pre-dose void and post-dose from 0-4 hours, 4-8 hours, 8-12 hours, and 12-24 hours; from 24-48 hours post-dose; from 48-72 hours post-dose; and from 72-96 hours post-dose. Samples are to be collected at intervals under colored lighting into opaque containers to blind participants to any discoloration of the urine.
- Spirometry performed on Days 2, 8, 10, and 12.
- Mandatory muscle biopsy on Day 14 (time 0) only.
- IPSS questionnaire will be performed at the specified timepoints per SOA- results greater than 8 will necessitate an unscheduled urinary system ultrasound as soon as is feasible.
- Urinary system Ultrasound will be performed at day 3, and days 7 and 14 at the 6-hour timepoint unless the IPSS result (greater than 8) necessitates additional unscheduled ultrasonography.
- Serum chemistry, eGFR, and calcium only.

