2.3. Nonclinical Studies and Interim Safety Analysis

Refer to the Investigator's Brochure (IB) or MTR-601 regarding nonclinical study data.

An unblinded interim safety analysis of SAD cohorts 1-4 and MAD cohorts 1-3 was performed to support further dose escalation above the 1/10th rat 28-day NOAEL level (where MAD dosing had been capped by the FDA). The key conclusions from that interim analysis were:

- In either single doses (10, 20, 40 and 80 mg) or repeat daily doses (10 and 20 mg for 14 days) MTR-601 did not demonstrate pharmacodynamic evidence of decreased muscle strength. This is likely because the achieved muscle concentrations (≤ 937 ng/mL) were below the estimated target for efficacy ($\geq 3,000$ ng/dL). Further dose escalation is required to adequately characterize MTR-601's pharmacodynamic effect.
- In both single and multiple doses, MTR-601 plasma pharmacokinetics were consistent and predictable, with linear dose-exposure proportionality, and modest (<2 -fold) accumulation at steady state. At the 20 mg level, steady state exposure (C_{max} and AUC_{0-24}) was approximately 1/15th of the NOAEL. MTR-601's well-behaved pharmacokinetics allows for reliable prediction of exposure for careful, continued dose escalation.
- In both single and multiple doses, MTR-601 was safe and very well tolerated, with no treatment-related AEs, and no clinically significant laboratory, ECG, or vital sign abnormalities. There were no MTR-601 associated abnormalities in plasma or urine markers of kidney function, and no objective or subjective evidence of urinary obstruction. This very good safety profile justifies continued dose escalation to more fully characterize MTR-601's clinical profile.

The findings of the interim safety evaluation support continued dose escalation to more fully characterize the PK, PD and safety of MTR-601.

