8.3. Safety Assessments

Safety assessments ([Table 8](#)) will include AEs and SAEs, as well as physical examinations, clinical laboratory evaluations, vital sign measurements, spirometry, urinary system ultrasound, Echocardiography, and ECGs. Not every assessment will be performed at each visit. Refer to the Schedule of Assessments ([Table 1](#), [Table 2](#), and [Table 3](#)) for specific procedures/assessments and timing. A separate schedule of permitted visit windows for each procedure/assessment will be provided in the Clinical Monitoring Plan and Data Management Plan

Note: When several assessments overlap, the suggested sequence of events will be as follows: ECG, vital sign collection, PK sample collection, laboratory blood sample collections, spirometry, dynamometry, urinalysis sample collection, and biopsy such that PK sample collection will be drawn as close to the nominal collection time point as possible. Echocardiography and Urinary system ultrasounds can be performed last so as to not delay the PK assessments.

Table 8: Safety Assessments

Assessment	Details
AE monitoring	Adverse events will be recorded from the first study medication dose through 14 days after the last follow-up visit/call. AEs will be graded using the scale in Section 8.4.4.3.
Physical examination	Physical examination and review of relevant systems at screening, including body weight and height. Symptom-directed physical examinations and weight measurements are to be performed at other time points or as clinically indicated.
Neurological exam	Includes cranial nerve assessments II-XII, cerebellar function (finger to nose and gait), reflexes (bilateral bicep, patellar, and ankle), gross assessment of extremity strength.
Vital signs	Systolic and diastolic blood pressure, heart rate, respiratory rate, and body temperature.
12-lead Electrocardiograms	The QTcF must be recorded for each ECG. All ECGs must be performed in triplicate with at least a 5 minute rest in the supine position with a minimum of 60 seconds in between and the average value will be used for interpretation and AE grade.
Left ventricular ejection fraction (LVEF)/ echocardiogram	An echocardiogram will measure ventricular volumes and left ventricular ejection fraction.

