8.4.7. Adverse Events of Special Interest (AESIs)

The myosin-2 isoform present in fast-twitch skeletal muscles and the extra-ocular muscles could be affected by MTR-601. Oculofacial AEs or any reduction in movement of the eyes, with potential for disconjugate gaze and “dizziness” or “imbalance” will be noted as an AESI. Additionally, AEs relating to swallowing or proximal muscle weakness (evaluated as part of the routine neurological examination) will be noted as an AESI. AEs related to reductions in eGFR, reductions in urinary output and/or urinary retention (via IPSS and Ultrasound) will be noted as an AESI.

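### In the MAD part, the neurological examination assigned to muscle-weakness AESIs is done on treatment only before dosing on Days 7 and 14, and Table 3 contradicts itself on strength testing before Day 7 in Cohorts 4-6

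*Protocol*

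**What the plan says.** Protocol Section 8.4.7 states that "AEs relating to swallowing or proximal muscle weakness (evaluated as part of the routine neurological examination) will be noted as an AESI"; Section 2.5 says the same. Table 8 in Section 8.3 describes the examination as covering cranial nerves II-XII, cerebellar function, reflexes and "gross assessment of extremity strength". Eye movement therefore also falls within it, although the protocol does not expressly tie the oculofacial AESIs to this examination.

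Table 3 (Section 1.5) schedules the examination in the MAD part at screening, Day -1, hour 0 of Days 7 and 14, and Day 18. Hour 0 is before the dose: "Plasma PK samples will be drawn at pre-dose (time 0) on Days 7 and 14".

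Strength is measured by dynamometry and magnetic stimulation. The Day 1 part of Table 3 marks dynamometry at 4, 8 and 12 h and magnetic stimulation at 4 h. Footnote p, attached to both rows there, gives Cohorts 4-6 a different list: "For Cohorts 4-6, Magnetic Stimulated Contraction and Dynamometry time points will be as follows: Day -1, Day 1 (0-2 hours pre-dose), Day 7", then Days 8, 12, 13, 14 and 15. It states no hour for any day after Day 1. The continuation of Table 3 is titled for Cohorts 1-6. Without footnote p, it marks dynamometry on the non-PK Days 2-6 and 8-13, and at 0, 4, 8 and 12 h on Days 7 and 14.

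Section 2.3 reports that single doses of 10 to 80 mg and 14-day dosing at 10 and 20 mg showed no loss of strength, and adds: "Further dose escalation is required to adequately characterize MTR-601's pharmacodynamic effect".

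**The concern.** MTR-601 is meant to inhibit fast skeletal myosin, so muscle weakness is the on-target risk, and the protocol names it as an AESI. The examination assigned to swallowing and proximal weakness is nevertheless scheduled, while subjects are on treatment, only at the end of the dosing interval. If weakness tracks plasma concentration, these examinations would tend to miss its maximum.

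For the repeat-dose cohorts above 20 mg, footnote p on its face also removes the early post-dose strength tests that partly cover this in Cohorts 1-3. Two things are at stake. One is the completeness of the AESI table planned in SAP Section 5.16.1. The other is the clinical information that reaches the Safety Review Committee (SRC). The only muscle-function criterion in the stopping rules (protocol Table 5) is forced vital capacity, so limb, swallowing or eye-muscle weakness reaches the SRC through adverse events and clinical findings.

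**Working it through.** The documents state no calculated figure on this point. The check is a count of schedule cells and a conversion of days to hours.

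**1. Timing of MAD neurological examinations after dosing starts** (Table 3; one dose daily on Days 1-14). Hours after first dose = (day − 1) × 24.

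| Examination | Hours after first dose | Hours since latest dose | Doses already given |
|---|---|---|---|
| Day 7, hour 0 | 6 × 24 = 144 | 24 | 6 |
| Day 14, hour 0 | 13 × 24 = 312 | 24 | 13 |
| Day 18 | 17 × 24 = 408 | (18 − 14) × 24 = 96 | 14 |

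No cell from 0.25 to 12 h is marked on any dosing day.

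**2. Strength sessions after the first dose and before Day 7 hour 0** (one session counted per marked non-PK day).

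| | Dynamometry | Magnetic stimulation |
|---|---|---|
| Cohorts 1-3, grid | 3 (Day 1) + 5 (Days 2-6) = 8 | 1 |
| Cohorts 4-6, footnote p replaces the grid | 0 | 0 |
| Cohorts 4-6, footnote p governs Day 1 and the unmarked continuation grid stands | 5 | 0 |

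The replacement reading is the more natural one. Footnote p is specific to these cohorts and adds magnetic stimulation on Days 8, 12 and 13, which the grid does not mark. The grid, however, also marks dynamometry on Days 16-18, which footnote p omits, and its title includes Cohorts 4-6. The text does not settle the matter. Even on the third row, the Days 2-6 column carries no hour, so a post-dose test before Day 7 is not assured.

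**3. What is new in Cohorts 4-6.** Three cohorts of 6 give 18 planned active subjects. Section 2.3 puts steady-state exposure at 20 mg at about 1/15 of the NOAEL exposure, with linear dose-exposure proportionality. Scaling linearly:

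- 40 mg: 2/15 = 0.13 of NOAEL exposure.
- 80 mg: 4/15 = 0.27.
- 160 mg: 8/15 = 0.53, above the protocol's cap of 1/2, so Cohort 6 would be limited to about (1/2) ÷ (1/15) = 7.5 times the 20 mg steady-state exposure.

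Single doses up to 80 mg have already been tested for strength without an effect. The main unknown is therefore repeat dosing above 20 mg.

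**4. How low is trough?** The documents give neither Tmax nor half-life, only accumulation of less than 2-fold, so this is an illustration under assumptions. In a one-compartment model with rapid absorption, the accumulation ratio is R = 1/(1 − e^(−kτ)), and trough/peak = e^(−kτ) = 1 − 1/R.

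- R = 1.3 (assumed): 1 − 1/1.3 = 0.23.
- R = 2.0 (upper bound): 1 − 1/2.0 = 0.50.

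Slower absorption would raise these values. The schedule finding does not depend on them.

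**5. What else could detect weakness.** Section 8.4.4.2 has each subject questioned about adverse events. Table 8 provides for symptom-directed examination. Spirometry is done on Days 1, 2, 7, 8, 10, 12 and 14; Days 1 and 2 fall before Day 7, but spirometry reflects respiratory muscle only.

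**The case against.** The case against has real weight.

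- **First doses are largely covered.** A Day 1 dose of 40 or 80 mg in the MAD part repeats what the SAD part tested without strength loss, and SAD Level 5 adds 160 mg as a single dose. This stands. It narrows the point to repeat dosing, which footnote p does test on Days 7, 8 and 12-15.
- **Strength after dosing may well be measured at steady state.** The grid has dynamometry at 4, 8 and 12 h and magnetic stimulation at 4 h on Days 7 and 14. If those hours apply to Cohorts 4-6, peak strength effect is observed. This stands as a likely intention, but footnote p does not state it.
- **Plasma trough may be the wrong measure.** Section 2.3 ties the efficacy target to muscle concentration. If effect follows muscle accumulation, testing from Day 7 is a sensible choice and the pre-dose timing matters less. Onset over Days 1-6 would still go unobserved under footnote p, and no reason is given for dropping the early tests.
- **Subjects are inpatients and are watched.** Questioning, symptom-directed examination and spirometry continue. This stands, and it limits the gap to scheduled, objective assessment.
- **The SRC's listed inputs in the study schema do not include dynamometry.** This stands for footnote p: an effect of the missing strength tests on escalation decisions is not shown. It does not apply to the neurological examination, which is part of the clinical data under review.

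**Conclusion.** The point holds in a limited form. In the MAD part the examination named for swallowing and proximal-weakness AESIs is done on treatment twice, both times 24 h after the previous dose, and first after six doses. For the 18 planned active subjects in Cohorts 4-6, Table 3 contradicts itself on whether strength is tested between the first dose and Day 7 (none, or five sessions without stated hours), and footnote p does not assure post-dose hours on Days 7 and 14.

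A reader might infer more than the documents support:

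- *That weakness before Day 7 would go undetected.* Three other routes remain.
- *That peak strength effect cannot be described.* The grid contains post-dose tests on Days 7 and 14.
- *That the absence of testing in Cohorts 4-6 is settled.* It depends on footnote p overriding the grid.
- *That the examination takes place at a known fraction of peak concentration.* Tmax and half-life are not given; 0.23 to 0.50 is an assumption-based range only.

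The conclusion rests on reading hour 0 as pre-dose, which the PK footnote supports. It is worth acting on because it concerns a named on-target risk at repeat doses not covered by the interim analysis, and the correction is nearly free.

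**What to change.** 1. In Table 3, move the Day 7 and Day 14 neurological examination from hour 0 to an existing post-dose slot. The 4 h slot already holds spirometry, C-SSRS, magnetic stimulation and dynamometry. Check the choice against the Tmax observed in the completed cohorts, because a late Tmax would make 4 h too early. The cost is loss of the pre-dose neurological check, though the hour-0 physical examination stays. On Day 14 the examination would follow the hour-0 thigh-muscle biopsy, as the grid's post-dose strength tests already do.

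2. Reconcile footnote p with the continuation grid: put the footnote mark on the rows it governs, or retitle the grid. State hours relative to dose for every Cohort 4-6 strength test, so that post-dose testing on Days 7 and 14 is assured and at least one post-dose test falls before Day 7. Repeat dosing is the main unknown, so a day after several doses may be more informative than Day 1. The cost is a few minutes per inpatient with equipment already in use, and a slight repeat-test effect.

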2. INTRODUCTION

2.1. Disease Background

Spasticity is a sensorimotor condition reflecting an abnormal increase in muscle tone or stiffness due to prolonged muscle contraction. It is usually caused by brain and spinal cord injuries after stroke or trauma or associated with neurological disorders like cerebral palsy or multiple sclerosis. Spasticity-related physical and mental effects can be severely disabling and render patients unable to walk, work, or carry out basic self-care.

There are multiple treatments available for spasticity, but most are characterized by limited efficacy and multiple side effects. Baclofen, a GABAB agonist, is a common centrally acting treatment for spasticity. While generally preferred as first-line treatment for spasticity, oral baclofen's efficacy is compromised by inefficient blood brain barrier penetration. Additionally, treatment is associated with unwelcome side effects, including systemic muscle relaxation, sedation, drowsiness and hepatotoxicity [1]. Intrathecal baclofen is used to achieve a higher central nervous system concentration and improve efficacy. Tizanidine, an α_2 agonist, is sometimes used in conjunction with other oral drugs, like baclofen, but its use is also limited by a very short half-life and multiple side effects, including sedation, hypotension, xerostomia, muscle weakness, hallucinations and QT interval prolongation [1]. Peripherally acting dantrolene has been associated with severe hepatotoxicity and its clinical use is limited [1]. Botulinum toxins are used to treat local spasticity, but treatments are painful, costly, inconvenient and often ineffective [2, 3]. Dorsal rhizotomy is a risky surgical treatment reserved for severe cases of spasticity.

Collectively, the limited efficacy and side effect profiles of available spasticity treatments highlight the need for a selective, well-tolerated, and effective oral treatment for spasticity.

MTR-601 directly targets the terminal effector enzyme (fast myosin-2 isoforms) of skeletal muscle contraction and, therefore, should be able to demonstrate efficacy without the neurological and cardiovascular side effect profile of current muscle relaxants. A further advantage of MTR-601-based muscle relaxation over current muscle relaxants is that MTR-601 does not cause complete immobilization even at extremely high doses due to the residual muscle tone from the uninhibited slow myosin-2 isoform fractions in skeletal muscles.

